14.3.3 Narratives of Deaths, Other Serious and Significant Adverse Events

[Placeholder for the CSR]

14.3.4 Abnormal Laboratory Value Listings (by Subject)**Table 192: Listing of Abnormal Laboratory Results – Chemistry**

Subject ID	Treatment Group	Baseline Flavivirus Immune Status	Sex	Age (years)	Planned Time Point	Actual Study Day	Laboratory Parameter (Units)	Result (Severity)	Relationship to Treatment	If Not Related, Alternate Etiology	Action Taken with Study Treatment	Subject Discontinued Due to Result?

Tables with similar format:

Table 193: Listing of Abnormal Laboratory Results – Hematology

Table 194: Listing of Abnormal Laboratory Results – Urinalysis

14.3.5 Displays of Laboratory Results

14.3.5.1 Chemistry Results

Table 195: Laboratory Results by Maximum Severity, Time Point, Treatment Group, and Baseline Flavivirus Immune Status – Any Chemistry Parameter

Time Point	Treatment Group	N	None		Mild/ Grade 1		Moderate/ Grade 2		Severe/ Grade 3		Missing	
			n	%	n	%	n	%	n	%	n	%
All Subjects												
Baseline	2.5 mcg ZPIV	x	x	xx	x	xx	x	xx	x	xx	x	xx
	5 mcg ZPIV											
	Placebo											
	All Subjects											
Repeat for:												
Day 8												
Day 15												
Day 36												
Day 43												
Max Severity Post Baseline												
Repeat for:												
Baseline ZIKV Seropositive												
Baseline ZIKV Seronegative												
Baseline ZIKV Seropositive and DENV Seropositive												
Baseline ZIKV Seropositive and DENV Seronegative												
Baseline ZIKV Seronegative and DENV Seropositive												
Baseline ZIKV Seronegative and DENV Seronegative												
N=Number of subjects in the Safety population who completed the specified visit.												
The “Max Severity Post Baseline” rows indicate the maximum severity experienced by each subject at any time point post baseline, including unscheduled assessments.												

Tables with similar format:

Table 196: **Laboratory Results by Maximum Severity, Time Point, Treatment Group, and Baseline Flavivirus Immune Status – ALT**

Table 197: **Laboratory Results by Maximum Severity, Time Point, Treatment Group, and Baseline Flavivirus Immune Status – AST**

Table 198: **Laboratory Results by Maximum Severity, Time Point, Treatment Group, and Baseline Flavivirus Immune Status – Total Bilirubin**

Table 199: **Laboratory Results by Maximum Severity, Time Point, Treatment Group, and Baseline Flavivirus Immune Status – BUN**

Table 200: **Laboratory Results by Maximum Severity, Time Point, Treatment Group, and Baseline Flavivirus Immune Status – Creatinine**

Table 201: Abnormal Laboratory Results Related to Study Treatment by Maximum Severity, Time Point, Treatment Group, and Baseline Flavivirus Immune Status – Any Chemistry Parameter

Time Point	Treatment Group	N	Mild/ Grade 1		Moderate/ Grade 2		Severe/ Grade 3	
			n	%	n	%	n	%
All Subjects								
Day 8	2.5 mcg ZPIV	x	x	xx	x	xx	x	xx
	5 mcg ZPIV							
	Placebo							
	All Subjects							
Repeat for:								
Day 15								
Day 36								
Day 43								
Max Severity Post Baseline								
Repeat for:								
Baseline ZIKV Seropositive								
Baseline ZIKV Seronegative								
Baseline ZIKV Seropositive and DENV Seropositive								
Baseline ZIKV Seropositive and DENV Seronegative								
Baseline ZIKV Seronegative and DENV Seropositive								
Baseline ZIKV Seronegative and DENV Seronegative								
N=Number of subjects in the safety population who completed the specified visit and results are available.								
The “Max Severity Post Baseline” rows indicate the maximum severity of abnormal laboratory results related to study treatment experienced by each subject at any time point post baseline, including unscheduled assessments.								

Tables with similar format:

Table 202: Abnormal Laboratory Results Related to Study Treatment by Maximum Severity, Time Point, Treatment Group, and Baseline Flavivirus Immune Status – ALT

Table 203: Abnormal Laboratory Results Related to Study Treatment by Maximum Severity, Time Point, Treatment Group, and Baseline Flavivirus Immune Status – AST

Table 204: Abnormal Laboratory Results Related to Study Treatment by Maximum Severity, Time Point, Treatment Group, and Baseline Flavivirus Immune Status – Total Bilirubin

Table 205: Abnormal Laboratory Results Related to Study Treatment by Maximum Severity, Time Point, Treatment Group, and Baseline Flavivirus Immune Status – BUN

Table 206: Abnormal Laboratory Results Related to Study Treatment by Maximum Severity, Time Point, Treatment Group, and Baseline Flavivirus Immune Status – Creatinine

Table 207: Laboratory Summary Statistics by Time Point and Treatment Group – ALT

Time Point	Treatment Group	N	Mean	Standard Deviation	Median	Min, Max
All Subjects						
Baseline	2.5 mcg ZPIV	xx	xx.x	xx.x	xx	xx, xx
	5 mcg ZPIV					
	Placebo					
	All Subjects					
Repeat for:						
Day 8						
Day 8, Change from Baseline						
Day 15						
Day 15, Change from Baseline						
Day 36						
Day 36, Change from Baseline						
Day 43						
Day 43, Change from Baseline						
Repeat for:						
Baseline ZIKV Seropositive						
Baseline ZIKV Seronegative						
Baseline ZIKV Seropositive and DENV Seropositive						
Baseline ZIKV Seropositive and DENV Seronegative						
Baseline ZIKV Seronegative and DENV Seropositive						
Baseline ZIKV Seronegative and DENV Seronegative						
N=Number of subjects in the Safety population who completed the specified visit and results are available.						

Tables with similar format:

Table 208: Laboratory Summary Statistics by Time Point and Treatment Group – AST

Table 209: Laboratory Summary Statistics by Time Point and Treatment Group – Total Bilirubin

Table 210: Laboratory Summary Statistics by Time Point and Treatment Group – BUN

Table 211: Laboratory Summary Statistics by Time Point and Treatment Group – Creatinine

14.3.5.2 Hematology Results

Table with format similar to Table 195:

Table 212: Laboratory Results by Maximum Severity, Time Point, Treatment Group, and Baseline Flavivirus Immune Status – Any Hematology Parameter

Table 213: Laboratory Results by Maximum Severity, Time Point, Treatment Group, and Baseline Flavivirus Immune Status – WBC

Time Point	Treatment Group	N	None		Mild/ Grade 1 (Low)		Mild/ Grade 1 (High)		Moderate/ Grade 2 (Low)		Moderate/ Grade 2 (High)		Severe/ Grade 3 (Low)		Severe/ Grade 3 (High)		Missing		
			n	%	n	%	n	%	n	%	n	%	n	%	n	%	n	%	
All Subjects																			
Baseline	2.5 mcg ZPIV	x	x	xx	x	xx	x	xx	x	xx	x	xx	x	xx	x	xx	x	xx	
	5 mcg ZPIV																		
	Placebo																		
	All Subjects																		
Repeat for:																			
Day 8																			
Day 15																			
Day 36																			
Day 43																			
Max Severity Post Baseline																			
Repeat for:																			
Baseline ZIKV Seropositive																			
Baseline ZIKV Seronegative																			
Baseline ZIKV Seropositive and DENV Seropositive																			
Baseline ZIKV Seropositive and DENV Seronegative																			
Baseline ZIKV Seronegative and DENV Seropositive																			
Baseline ZIKV Seronegative and DENV Seronegative																			
N=Number of subjects in the Safety population who completed the specified visit.																			
The “Max Severity Post Baseline” rows indicate the maximum severity experienced by each subject at any time point post baseline, including unscheduled assessments.																			

Table with format similar to Table 195:

Table 214: Laboratory Results by Maximum Severity, Time Point, Treatment Group, and Baseline Flavivirus Immune Status–Hemoglobin

Table with format similar to Table 213:

Table 215: Laboratory Results by Maximum Severity, Time Point, Treatment Group, and Baseline Flavivirus Immune Status–Hematocrit

Table with format similar to Table 195:

Table 216: Laboratory Results by Maximum Severity, Time Point, Treatment Group, and Baseline Flavivirus Immune Status–Platelet Count

Table with format similar to Table 201:

Table 217: Abnormal Laboratory Results Related to Study Treatment by Maximum Severity, Time Point, Treatment Group, and Baseline Flavivirus Immune Status – Any Hematology Parameter

Table 218: Abnormal Laboratory Results Related to Study Treatment by Maximum Severity, Time Point, Treatment Group, and Baseline Flavivirus Immune Status– WBC

Time Point	Treatment Group	N	Mild/ Grade 1 (Low)		Mild/ Grade 1 (High)		Moderate/ Grade 2 (Low)		Moderate/ Grade 2 (High)		Severe/ Grade 3 (Low)		Severe/ Grade 3 (High)	
			n	%	n	%	n	%	n	%	n	%	n	%
All Subjects														
Day 8	2.5 mcg ZPIV	X	X	XX	X	XX	X	XX	X	XX	X	XX	X	XX
	5 mcg ZPIV													
	Placebo													
	All Subjects													
Repeat for:														
Day 15														
Day 36														
Day 43														
Max Severity Post Baseline														
Repeat for:														
Baseline ZIKV Seropositive														
Baseline ZIKV Seronegative														
Baseline ZIKV Seropositive and DENV Seropositive														
Baseline ZIKV Seropositive and DENV Seronegative														
Baseline ZIKV Seronegative and DENV Seropositive														
Baseline ZIKV Seronegative and DENV Seronegative														
N=Number of subjects in the safety population who completed the specified visit and results are available.														
The “Max Severity Post Baseline” rows indicate the maximum severity of abnormal laboratory results related to study treatment experienced by each subject at any time point post baseline, including unscheduled assessments.														

Table with format similar to Table 201:

Table 219: Abnormal Laboratory Results Related to Study Treatment by Maximum Severity, Time Point, Treatment Group, and Baseline Flavivirus Immune Status – Hemoglobin

Table with format similar to Table 218:

Table 220: Abnormal Laboratory Results Related to Study Treatment by Maximum Severity, Time Point, Treatment Group, and Baseline Flavivirus Immune Status – Hematocrit

Table with format similar to Table 201:

Table 221: Abnormal Laboratory Results Related to Study Treatment by Maximum Severity, Time Point, Treatment Group, and Baseline Flavivirus Immune Status – Platelet Count

Tables with format similar to Table 207:

Table 222: Laboratory Summary Statistics by Time Point and Treatment Group – WBC

Table 223: Laboratory Summary Statistics by Time Point and Treatment Group – Hemoglobin

Table 224: Laboratory Summary Statistics by Time Point and Treatment Group – Hematocrit

Table 225: Laboratory Summary Statistics by Time Point and Treatment Group – Platelet Count

14.3.5.3 Urinalysis Results

Tables with format similar to Table 195:

Table 226: **Laboratory Results by Maximum Severity, Time Point, Treatment Group, and Baseline Flavivirus Immune Status – Any Urinalysis Parameter**

Table 227: **Laboratory Results by Maximum Severity, Time Point, Treatment Group, and Baseline Flavivirus Immune Status – Urine Protein**

Table 228: **Laboratory Results by Maximum Severity, Time Point, Treatment Group, and Baseline Flavivirus Immune Status – Urine Glucose**

Tables with format similar to Table 201:

Table 229: **Abnormal Laboratory Results Related to Study Treatment by Maximum Severity, Time Point, Treatment Group, and Baseline Flavivirus Immune Status – Any Urinalysis Parameter**

Table 230: **Abnormal Laboratory Results Related to Study Treatment by Maximum Severity, Time Point, Treatment Group, and Baseline Flavivirus Immune Status – Urine Protein**

Table 231: **Abnormal Laboratory Results Related to Study Treatment by Maximum Severity, Time Point, Treatment Group, and Baseline Flavivirus Immune Status – Urine Glucose**

14.3.6 Displays of Vital Signs**Table 232: Vital Signs by Maximum Severity, Time Point and Treatment Group – Any Assessment**

Time Point	Treatment Group	N	None		Mild/ Grade 1		Moderate/ Grade 2		Severe/ Grade 3		Any Severity	
			n	%	n	%	n	%	n	%	n	%
Baseline	2.5 mcg ZPIV	xx	xx	xx	xx	xx	xx	xx	xx	xx	xx	xx
	5 mcg ZPIV											
	Placebo											
	All Subjects											
Repeat for:												
Day 1												
Day 2												
Day 8												
Day 15												
Day 29												
Day 30												
Day 36												
Day 43												
Day 57												
Max Severity Post Baseline												

N=Number of subjects in the Safety population who completed the specified visit and have any vital signs data available from the visit.
The “Max Severity Post Baseline” rows indicates the maximum severity experienced by each subject at any time point post baseline, including unscheduled assessments.

Tables with similar format:

Table 233: Vital Signs by Maximum Severity, Time Point and Treatment Group – Oral Temperature

Table 234: Vital Signs by Maximum Severity, Time Point and Treatment Group – Pulse

Table 235: Vital Signs by Maximum Severity, Time Point and Treatment Group – Systolic Blood Pressure

Table 236: Vital Signs by Maximum Severity, Time Point and Treatment Group – Diastolic Blood Pressure

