## **8.2 Study Enrollment and First Vaccination Visit**

### **8.2.1 Visit 01, Study Day 1, Enrollment and First Vaccination**

- Reconfirm subject's willingness to participate prior to performing any study procedures, including consent for future use of samples prior to administration of the first study vaccination.
- Perform a urine pregnancy test within 24 hours prior to study vaccine administration on all female subjects of childbearing potential. Results must be known and negative prior to enrollment and receipt of study vaccine.
- Review eligibility criteria, including results of all screening laboratory tests, prior to the first study vaccination to assure continued eligibility.
  - If the initial screening laboratory tests are more than 28 days old, these tests will need to be repeated (see [Section 7.2.1](#)). However, repeat testing for HIV, HCV, and HBV are not needed.
- Review medical history and any updates obtained by interview of subjects since the screening visit to assure continued eligibility.

- Ask about febrile/rash illness. If the subject reports history of AFI/ARI within the past 14 days, conduct a febrile/rash illness assessment and sample collection as per [Section 8.7](#).
- Review all concomitant medications and recent vaccinations (within 30 days of signing the ICF) with subjects prior to the first vaccination for accuracy and completeness. Any new medications taken since the screening visit will be recorded on the appropriate case report form and assessed for continued eligibility.
- Vital signs including oral temperature, blood pressure, and pulse, will be obtained prior to the first study vaccination.
- Perform a targeted physical examination prior to the first study vaccination, if indicated based on review of complete medical history and updates obtained by interview of subjects since the screening visit.
- Collect blood samples for, humoral immunity, HLA typing, CPT tubes and a Paxgene tube prior to vaccination.
- Enroll and randomize subjects in Advantage EDC prior to the first study vaccination.
- Perform pre-administration reactogenicity assessment prior to the first study vaccination to establish baseline. Subjects will then receive a single dose of study vaccine via IM injection into the deltoid muscle of the preferred arm. The site of injection (right or left arm) and time of administration will be recorded on the case report form.

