# Pulse and blood pressure assessed on Screening will be considered as baseline.

### **Clinical Safety Laboratory Adverse Event Grading**

*Note: Ranges have been modified to reflect local laboratory normal ranges for the sites conducting this study*

Hematology	Mild (Grade 1)	Moderate (Grade 2)	Severe (Grade 3)
WBC 10  /UL (Decrease)	2.5 – 3.4	1.5 – 2.4	<1.5
WBC 10  /UL (Increase)	10.9 – 15.0	15.1 – 20.0	>20.0
HgB g/dL Female	10.5-11.4	8.5-10.4	<8.5
HgB g/dL Male	12.0-13.4	10.0-11.9	<10.0
HCT % decrease Female	31.5-34.2	25.5-31.4	<25.5
HCT % decrease Male	36.0-40.2	30-35.9	<30
HCT % increase	1.01-1.1 X ULN	1.11-1.2 X ULN	>1.2 X ULN
Platelets cell/10  /UL (Decrease)	100-149	99-75	<75

Chemistry	Mild (Grade 1)	Moderate (Grade 2)	Severe (Grade 3)
ALT	1.25 – 3.0 x ULN	>3.0 – 5.0 x ULN	>5.0 x ULN
AST	1.25 – 3.0 x ULN	>3.0 – 5.0 x ULN	> 5.0 x ULN
Bilirubin – when ALT $\geq$ 3 x ULN	1.25 – 1.5 x ULN	>1.5 – 2.0 x ULN	>2.0 x ULN
Bilirubin	1.25 – 2.0 x ULN	>2.0 – 2.5 x ULN	>2.5 x ULN
BUN mg/dL	26-30	31-35	> 35
Creatinine mg/dL	1.1 – 1.7	1.8 – 2.0	>2.0

Urine Dipstick	Mild (Grade 1)	Moderate (Grade 2)	Severe (Grade 3)
-----------------------	---------------------------	-------------------------------	-----------------------------

Protein	1+	2+	>2+
Glucose	1+	2+	>2+

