3.3. Study Definitions and Derived Variables

Baseline Values

Unless otherwise specified, baseline values will be defined as the last values obtained prior to the first investigational vaccination. Vital signs (pulse and blood pressure) assessed at screening will be considered as baseline. Any medical condition that is present at the time that the subject is screened will be considered as baseline and not reported as an adverse event.

Adverse Events of Special Interest

For this study, Neurologic and Neuroinflammatory Disorders will be considered as adverse events of special interest (AESI). These include Acute Disseminated Encephalomyelitis (ADEM, including site specific variants), Cranial Nerve Disorders (including paralyses/paresis), Guillain-Barre Syndrome (GBS, including Miller Fisher Syndrome and other variants), Immune-mediated Peripheral Neuropathies and Plexopathies, Optic Neuritis, Multiple Sclerosis, Narcolepsy, Transverse Myelitis, meningitis, or meningoencephalitis.

Baseline Flavivirus Immune Status

Subjects enrolled in the study will have blood drawn during the screening visit (Visit 00) or pre-vaccination at the first visit (Visit 01) to determine baseline flavivirus immune status. Serum will be tested via serology for antibodies to ZIKV and DENV. Baseline flavivirus immune status will be treated as a categorical variable and will be used to stratify tables and figures throughout the analyses specified in this SAP. The goal of determining the baseline flavivirus status is to see if there is an effect of baseline flavivirus seropositivity on response to ZPIV. With this in mind, subjects are categorized initially at ZIKV seropositive (based on a positive IgM or IgG assay pre-vaccination) or ZIKV seronegative (based on negative IgM and IgG tests pre-vaccination). Subjects are then subcategorized as DENV seropositive or seronegative, within each ZIKV category.

Baseline flavivirus immune status will be defined primarily as follows:

- ZIKV Seropositive: any subject with detectable ZIKV antibodies pre-vaccination
- ZIKV Seronegative: any subject without detectable ZIKV antibodies pre-vaccination

Baseline flavivirus immune status will then be further classified into the following groups:

- ZIKV Seropositive and DENV Seropositive
- ZIKV Seropositive and DENV Seronegative
- ZIKV Seronegative and DENV Seropositive
- ZIKV Seronegative and DENV Seronegative

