4.5. Immunogenicity and Safety Variables

In general, multiple observations within a specific visit period were accepted. In the case of multiple observations within a specific window, the assessment value closest to the scheduled visit date will be used in the analyses for the post-baseline records. If observations have the same distance to the scheduled assessment, the latest one will be used. Unless otherwise specified, the last assessment value recorded prior to the prime dose will be used as baseline. All the recorded data will be listed. Samples from days on which a subject was vaccinated were collected prior to vaccination.

All subjects were to have venous blood samples for assessment of humoral immunity collected on Days 1, 15, 29, 43, 57, 209, 388, and 569. Assay results are reported as the ZIKV titers giving 50% reduction in viral infection (MN50) and IgG ELISA titers. DENV neutralization titers were also to be recorded in subjects reporting ARI or AFI. Samples from the immunogenicity visits immediately before and after the illness visit were used to measure DENV titers, which will be used to aid laboratory confirmation of ZIKV/DENV infection.

Solicited adverse events were collected from the time of study vaccine administration through Day 8 after each dose. Subjects received a memory aid to record any solicited AEs on each day. The following injection site reactogenicity events were measured and grading according to the scale in [Table 3](#) and [Table 4](#): pain, tenderness, pruritis, ecchymosis, erythema, and induration. The following systemic solicited events were measured and graded according to the scale in [Table 4](#) and [Table 5](#): feverishness, fatigue, malaise, myalgia, arthralgia, headache, nausea, vomiting, diarrhea, abdominal pain, rash, and fever.

Vital signs of heart rate and blood pressure were measured in subjects at Days 1, 2, 8, 15, 29, 30, 36, 43, and 57. The measurements were assessed for adverse events of bradycardia/tachycardia and systolic and diastolic hypotension/hypertension according to the scale in [Table 6](#).

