Headache		Some interference with daily activity or it requires > 24 hours of use of non-narcotic pain medication	Significant interference, prevents daily activity or it requires any use of narcotic pain medication
Nausea Vomiting Diarrhea Abdominal Pain Rash*		Some interference with daily activity	Significant interference, prevents daily activity

* Not at injection site.

Table 5: Quantitative Systemic Reactogenicity Grading

Systemic (Quantitative)	Mild (Grade 1)	Moderate (Grade 2)	Severe (Grade 3)
Fever [#] - oral [†]	38.0°C – 38.4°C 100.4°F – 101.1°F	38.5°C – 38.9°C 101.2°F – 102.0°F	>38.9°C >102.0°F

Oral temperature assessed on Day 1 prior to the first study vaccination will be considered as baseline.

[#] A fever can be considered not related to the study vaccine if an alternative etiology can be documented.

[†] Subjects must not eat or drink anything hot or cold, or smoke within 10 minutes prior to taking oral temperature

Table 6: Vital Sign Adverse Event Grading Scale

Physiologic Parameter	Mild (Grade 1)	Moderate (Grade 2)	Severe (Grade 3)
Bradycardia - beats per minute	50 – 54 (or 45 – 49 if baseline < 60)	45 – 49 (or 40 – 44 if baseline < 60)	<45 (or <40 if baseline < 60)
Tachycardia - beats per minute	101 – 115	116 – 130	>130 (or ventricular dysrhythmias)
Hypotension (systolic) mm Hg	85 – 89	80 – 84	<80
Hypotension (diastolic) mm Hg	50 – 54	45 – 49	<45
Hypertension (systolic) mm Hg	141 – 150	151 – 160	>160
Hypertension (diastolic) mm Hg	91 – 95	96 – 100	>100
#Pulse and blood pressure assessed at screening will be considered as baseline.			

Table 7: Laboratory Adverse Event Grading Scale

	Mild (Grade 1)	Moderate (Grade 2)	Severe (Grade 3)
Hematology			
WBC 10 ³ /UL (Decrease)	2.5 – 3.4	1.5 – 2.4	<1.5
WBC 10 ³ /UL (Increase)	10.9 – 15.0	15.1 – 20.0	>20.0
HgB g/dL Female	10.5-11.4	8.5-10.4	<8.5
HgB g/dL Male	12.0-13.4	10.0-11.9	<10.0
HCT % decrease Female	31.5-34.2	25.5-31.4	<25.5
HCT % decrease Male	36.0-40.2	30-35.9	<30
HCT % increase	1.01-1.1 X ULN	1.11-1.2 X ULN	>1.2 X ULN
Platelets cell/10 ³ /UL (Decrease)	100-149	99-75	<75
Chemistry			
ALT	1.25 – 3.0 x ULN	>3.0 – 5.0 x ULN	>5.0 x ULN
AST	1.25 – 3.0 x ULN	>3.0 – 5.0 x ULN	> 5.0 x ULN
Bilirubin– when ALT \geq 3 x ULN	1.25 – 1.5 x ULN	>1.5 – 2.0 x ULN	>2.0 x ULN
Bilirubin	1.25 – 2.0 x ULN	>2.0 – 2.5 x ULN	>2.5 x ULN
BUN mg/dL	26-30	31-35	> 35
Creatinine mg/dL	1.1 – 1.7	1.8 – 2.0	>2.0
Urine Dipstick			
Protein	1+	2+	>2+
Glucose	1+	2+	>2+

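### For pulse and blood pressure, the SAP's Max Severity Post Baseline row takes in the Day 1 reading made before the first vaccination

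*SAP*

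**What the plan says.** SAP section 9.7 presents abnormal vital signs by visit, treatment group and severity in Table 232 (any assessment) and Tables 233 to 236 (oral temperature, pulse, systolic and diastolic pressure). The Table 232 shell, which the other four share, has a Baseline row, then rows for Day 1 to Day 57, then a row called Max Severity Post Baseline. Its footnote defines that row as the "maximum severity experienced by each subject at any time point post baseline", and counts unscheduled assessments too.

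Four other statements decide what the row contains:

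- SAP 3.3 sets a default: "Unless otherwise specified, baseline values will be defined as the last values obtained prior to the first investigational vaccination". It then makes an exception: "Vital signs (pulse and blood pressure) assessed at screening will be considered as baseline". Protocol 9.2.3 agrees: "Pulse and blood pressure assessed on Screening will be considered as baseline".
- For temperature, the note to SAP Table 5 says: "Oral temperature assessed on Day 1 prior to the first study vaccination will be considered as baseline".
- Protocol 8.2.1 says of the Day 1 visit: "Vital signs including oral temperature, blood pressure, and pulse, will be obtained prior to the first study vaccination".
- SAP 4.5 lists the schedule: "Vital signs of heart rate and blood pressure were measured in subjects at Days 1, 2, 8, 15, 29, 30, 36, 43, and 57".

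**The concern.** A reader of a cumulative safety row will usually take it to describe what happened after vaccination. Here baseline for pulse and blood pressure can lie up to 28 days before dosing, and a pre-dose visit falls between baseline and the first injection. A raised pulse or blood pressure at that visit cannot have been caused by the product, yet it satisfies the definition of the row.

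Safety is the primary objective, and this row is the only cumulative vital-sign summary in these tables. The arms are small and unequal: about 45 on 5 mcg, 35 on 2.5 mcg and 10 on placebo. A few pre-dose readings could therefore change the displayed contrast by chance, although the rule is the same in every arm.

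**Working it through.** The plan gives no figure to reproduce. The check is first one of definitions, then an illustration of size.

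**Step 1. Which readings enter the row?**

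| Measure | Baseline | Day 1 pre-dose reading is | Pre-dose scheduled readings in the row |
|---|---|---|---|
| Pulse, systolic, diastolic (Tables 234–236) | Screening | after baseline | 1 of 9 |
| Any assessment (Table 232) | Mixed | after baseline for pulse and blood pressure | inherited from pulse and blood pressure |
| Oral temperature (Table 233) | Day 1, pre-dose | the baseline itself | 0 |

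The nine scheduled days are 1, 2, 8, 15, 29, 30, 36, 43 and 57. Eight follow the first vaccination. Protocol 8.2.1 schedules no second set of vital signs on Day 1: the 30-minute observation covers acute reactions, the injection site and reactogenicity. Neither SAP 9.7 nor any table note limits the row to readings after dosing.

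**Step 2. Can a graded reading occur on Day 1?** Yes. Eligibility requires vital signs that are normal on the grading scale or judged a normal variant by the investigator, so a graded value can pass. The schedule notes also allow one repeat when the Day 1 reading is abnormal. SAP 4.5 resolves two readings equally close to the visit date in favour of the later one. It does not say whether the abnormal first reading still counts in a row that takes in unscheduled assessments.

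**Step 3. How large could the effect be?** The documents give no per-visit abnormality rate, so p below is an assumption. With independent visits and the same p at each, the share of subjects with at least one abnormal value is 1 − (1 − p)^n. The excess due to Day 1 is [1 − (1 − p)^9] − [1 − (1 − p)^8] = p(1 − p)^8.

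| Assumed p | 8 post-dose visits | 9 visits with Day 1 | Excess (points) | Of 90 subjects |
|---|---|---|---|---|
| 1% | 7.7% | 8.6% | 0.9 | 0.8 |
| 2% | 14.9% | 16.6% | 1.7 | 1.5 |
| 5% | 33.7% | 37.0% | 3.3 | 3.0 |
| 10% | 57.0% | 61.3% | 4.3 | 3.9 |
| 20% | 83.2% | 86.6% | 3.4 | 3.0 |

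The expression p(1 − p)^8 is largest at p = 1/9, where it is (1/9)(8/9)^8 = 0.043. Under this model the excess therefore cannot pass about 4.3 points.

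**Step 4. Relaxing the two assumptions, at p = 5%.**

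- Correlated visits, using a beta-binomial with assumed intraclass correlation r: put s = (1 − r)/r and b = (1 − p)s. The chance of no abnormality in n visits is the product of (b + i)/(s + i) for i = 0 to n − 1. With r = 0.1 the share goes from 26.2% to 28.2%, an excess of 2.0 points. With r = 0.3 it goes from 17.9% to 18.9%, an excess of 0.9 points.
- Day 1 cleaner than other visits: with independent visits and an assumed Day 1 rate of 1%, the excess is 0.01 × 0.95^8 = 0.0066, or 0.7 points. That is 0.6 of 90 subjects.

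These figures concern any abnormality. A Day 1 value could also raise the grade of a subject already counted, which they do not capture.

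**Step 5. One subject's weight by arm.** One subject whose only abnormality was pre-dose moves the rate by 1/45 = 2.2 points on 5 mcg, 1/35 = 2.9 points on 2.5 mcg and 1/10 = 10 points on placebo.

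**The case against.** The best defence is that the row is labelled post baseline, which is accurate under the stated baseline, and that the screening baseline is the protocol's own choice. Day 1 already has its own row, Listing 20 gives individual values, and every visit is shown by arm and grade. No primary endpoint names vital signs, the overall adverse event summary (Table 36) has no vital-sign line, and no between-arm test of them is planned. SAP 9.7 describes Listing 20 as covering readings after treatment administration, which hints that a post-dose summary was intended.

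Most of this stands and limits the importance of the point. It does not remove it. The Day 1 row lets a reader see how many abnormalities were pre-dose, but not how many subjects are in the cumulative row for that reason alone. The hint about Listing 20 does not settle intent, because the listing's own shell says it includes all assessments.

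A reader might also infer that vital signs follow a different baseline rule from the laboratory tests. The documents do not support that. SAP 9.6 treats the screening laboratory results as baseline, and no safety laboratory draw is scheduled on Day 1. The same footnote wording is harmless in the laboratory tables because their first scheduled post-baseline visit is Day 8.

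**Conclusion.** The point holds for pulse, systolic and diastolic pressure, and for the any-assessment table through them. As defined, the row admits one pre-dose reading out of nine scheduled. This follows from putting the definitions together; the SAP does not state the inclusion in words.

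Three stronger readings are not supported:

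- That all five tables are affected. Table 233 is not, since the Day 1 pre-dose temperature is its baseline.
- That the plan labels pre-dose readings as post-vaccination. It does not, though a reader could take the row that way.
- That one arm is favoured or a product effect is hidden. The rule applies equally to all arms, so any imbalance would arise by chance.

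The size is unknown. About 1 to 4 percentage points follows from assumed rates of 1% to 10% per visit with independent visits and Day 1 as often abnormal as any other day. Plausible departures from those assumptions make it smaller. The case for changing the row is that it counts readings the product cannot have caused and that the correction costs very little.

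**What to change.** In Tables 232 and 234 to 236, rename the last row Max Severity Post First Vaccination. Define it as the highest grade at scheduled visits from Day 2 onward plus any unscheduled assessment after dose 1. Label the existing Day 1 row as pre-dose. State that repeat readings made before the first vaccination do not enter the maximum. Day 29 readings stay in, since they follow dose 1.

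Table 233 needs no change to its maximum. Its Day 1 row merely duplicates Baseline and could be dropped or footnoted. The screening baseline for pulse and blood pressure need not change.

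The cost is a revised footnote, two row labels and a date and time filter in the table program. No new data are needed.
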